Multiple System Atrophy (MSA) is a progressive and fatal neurodegenerative disease. MSA is characterized pathologically by glial cytoplasmic inclusions (GCIs) that consist of ectopic aggregates of hyperphosphorylated and insoluble filamentous α-synuclein in oligodendrocytes (Tu PH, 1998) and selective neurodegeneration in the striatonigral and olivopontocerebellar regions. Microglial activation parallels the neurodegeneration and GCI pathology in MSA (Ishizawa K, 2004).

Clinically, the cardinal features include autonomic failure, parkinsonism, cerebellar ataxia, and pyramidal signs in any combination. Two major motor presentations can be distinguished clinically. Parkinsonian features predominate in 80% of patients (MSA-P subtype), whereas cerebellar ataxia predominates in the remaining 20% of patients (MSA-C subtype). MSA is a progressive disorder with early disability and shortened life expectancy.

No cures are available and treatment is symptomatic. Levodopa is used to manage the motor symptoms, but patients become rapidly irresponsive to this drug due to widespread glial and neuronal cell degeneration and shrinkage of some brain areas such as cerebellum, basal ganglia and brainstem with eventual death within 9-10 years after diagnosis. Pain is a common non-motor symptom both in PD and MSA (Kass-Iliyya, 2015).

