4.2. Scientific Rationale for Study Design

This study is a randomized, double blind, trial to provide scientific rigor to minimize the chance of bias in the results. The trial duration is sufficiently long to establish safety, tolerability, and possible symptomatic benefits, yet short enough for disease progression not to be a confounding factor.

Justification for the use of placebo in addition to background standard of care (SoC) therapy is based on Zambon S.P.A. interpretation and position with regard to the ICH Topic E10 guideline on the "Choice of control group in clinical trials" (CPMP/ICH/364/96) and is in accordance with the EMA position for "Use of placebo in clinical trials with regard to the revised Declaration of Helsinki" (EMEA/17424/01).

The sponsor believes that placebo can be safely and ethically administered in this study based on the following rationale:

- All patients, whether in the active or placebo group, will continue using MSA treatment including levodopa; the investigational product will be added to the patient's standard therapy.
- Prior and concomitant medications which are considered necessary for the safety and well-being of the subject are permitted during the study at the discretion of the investigator provided the medication is not listed within the study exclusion criteria or in the excluded medication. If a subject is treated with a prohibited medication, a decision will be taken on whether or not the subject should continue in the study.

The treatment duration is sufficiently long to potentially show symptomatic efficacy, yet short enough that disease progression is unlikely to be a confounder.

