8.3.6. Disease-Related Events and/or Disease-Related Outcomes Not Qualifying as AEs or SAEs

Not applicable

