8.4. Treatment of Overdose

The anticipated pattern of events or symptoms following intentional or accidental overdose with safinamide is that related to its pharmacodynamic profile (MAO-B inhibition with activity dependent inhibition of sodium channels). The symptoms of excessive MAO-B inhibition (increase in dopamine level) could include hypertension, postural hypotension, hallucinations, agitation, nausea, vomiting and dyskinesia.

There is no known antidote to safinamide or any specific treatment for a safinamide overdose. If a significant overdose should occur, safinamide treatment should be discontinued and supportive treatment should be administered as clinically indicated.

In the event of an overdose, the Investigator should:

- Contact the Medical Monitor immediately.
- Closely monitor the participant for any AE/SAE or laboratory abnormalities
- Obtain a plasma sample for PK analysis if requested by the Medical Monitor (determined on a case-by-case basis).
- Document the quantity of the excess dose as well as the duration of the overdose in the CRF

Decisions regarding dose interruptions or modifications will be made by the investigator in consultation with the Medical Monitor based on the clinical evaluation of the participant.

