9.4.1. Safety Analyses

The primary objective of this study is to evaluate the safety and tolerability of safinamide, 200 mg od, compared with placebo.

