- Any abnormal laboratory test results (hematology, clinical chemistry, or urinalysis) or other safety assessments (eg, ECG, radiological scans, vital signs measurements), including those that worsen from baseline, considered clinically significant in the medical and scientific judgment of the investigator (ie, not related to progression of underlying disease).
- Exacerbation of a chronic or intermittent pre-existing condition including either an increase in frequency and/or intensity of the condition.
- New conditions detected or diagnosed after study intervention administration even though it may have been present before the start of the study.
- Signs, symptoms, or the clinical sequelae of a suspected drug-drug interaction.
- Signs, symptoms, or the clinical sequelae of a suspected overdose of either study intervention or a concomitant medication. Overdose per se will not be reported as an AE/SAE unless it is an intentional overdose taken with possible suicidal/self-harming intent. Such overdoses should be reported regardless of sequelae.
- "Lack of efficacy" or "failure of expected pharmacological action" per se will not be reported as an AE or SAE. Such instances will be captured in the efficacy assessments. However, the signs, symptoms, and/or clinical sequelae resulting from lack of efficacy will be reported as AE or SAE if they fulfil the definition of an AE or SAE.

Events NOT Meeting the AE Definition

- Any clinically significant abnormal laboratory findings or other abnormal safety assessments which are associated with the underlying disease, unless judged by the investigator to be more severe than expected for the participant's condition.
- The disease/disorder being studied or expected progression, signs, or symptoms of the disease/disorder being studied, unless more severe than expected for the participant's condition.
- Medical or surgical procedure (e.g., endoscopy, appendectomy): the condition that leads to the procedure is the AE.
- Situations in which an untoward medical occurrence did not occur (social and/or convenience admission to a hospital).
- Anticipated day-to-day fluctuations of pre-existing disease(s) or condition(s) present or detected at the start of the study that do not worsen.

Definition of SAE

If an event is not an AE per definition above, then it cannot be an SAE even if serious conditions are met (e.g., hospitalization for signs/symptoms of the disease under study, death due to progression of disease).

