#### 3.5.1 Adverse Events (AEs)

An overview of AEs will be provided including counts and percentages of subjects with the following:

- Any TEAEs (overall and by maximum severity)
- Any study drug related TEAEs
- Any serious TEAEs (SAEs)
- Any TEAEs leading to dose interruption
- Any TEAEs leading to dose reduction
- Any TEAEs leading to discontinuation of study drug
- Any AEs leading to death

Counts and percentages of subjects will also be presented by system organ class and preferred term for TEAEs, SAEs, study drug related TEAEs, and TEAEs leading to discontinuation of study drug.

Listings will be presented for all TEAEs, SAEs, and study drug related TEAEs.

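### Appendix 3 lets expected MSA events, including hospitalisations and progression deaths, stay out of the AE and SAE tables by investigator judgement, and it conflicts with Protocol 8.3.6 and SAP 3.5 and 5

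*Protocol*

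**What the plan says.** Protocol 9.4.1 states the purpose of the trial: "The primary objective of this study is to evaluate the safety and tolerability of safinamide, 200 mg od, compared with placebo".

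Appendix 3 (Protocol 10.3) then limits what counts as an adverse event. Its list of events that do not qualify includes "The disease/disorder being studied or expected progression, signs, or symptoms of the disease/disorder being studied, unless more severe than expected" for the participant's condition. A parallel entry excludes abnormal laboratory or other safety findings associated with the underlying disease, with the same exception. The SAE definition follows from this: a non-AE "cannot be an SAE even if serious conditions are met (e.g., hospitalization for signs/symptoms of the disease under study", with death due to progression as the other example.

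The same appendix also points the other way. It defines an AE without regard to relationship to study drug, and it lists as an AE any pre-existing condition that becomes more frequent or more intense.

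Three other places bear on the rule:
- Protocol 8.3.6, headed "Disease-Related Events and/or Disease-Related Outcomes Not Qualifying as AEs or SAEs", is answered as not applicable.
- SAP 3.5 says that any abnormal laboratory result or other safety assessment will be reported as an AE. SAP 5 drops the protocol's shift tables on that ground.
- The SAP 3.5.1 overview counts TEAEs, serious TEAEs and "Any AEs leading to death". Each row can hold only events first recorded as AEs.

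**The concern.** The rule acts before any comparison between arms. An event judged to be expected MSA is not entered as an AE. It then never reaches the causality assessment, SAE reporting or the TEAE and SAE tables. No list or criterion in the documents says what is expected, and Protocol 1.1 foresees no independent monitoring committee.

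This matters because disease and drug can look alike in a single patient. The Introduction says of MSA that "the cardinal features include autonomic failure, parkinsonism, cerebellar ataxia, and pyramidal signs in any combination". Protocol 8.4, on overdose, says the symptoms of excessive MAO-B inhibition "could include hypertension, postural hypotension, hallucinations, agitation, nausea, vomiting and dyskinesia". An orthostatic event leading to hospitalisation could belong to either. Randomisation can separate the two across arms, but only if the events are kept in the data.

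At stake is the completeness of the serious-event data behind the primary objective. Protocol 9.2 justifies the sample as enough to estimate whether the AE excess over placebo stays within the range of less than 10% seen in Parkinson's disease. A filter on AEs bears directly on that quantity.

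**Working it through.** **Planned numbers.** 48 randomised at 2:1 gives 48 × 2/3 = 32 and 48 × 1/3 = 16. The stated 40 evaluable would split 26.7 and 13.3, against the plan's 26 and 14, so the plan's figures reproduce. The safety population is close to 32 and 16.

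**Rates.** The only MSA rates in the documents are those of the rasagiline trial in Protocol 2.2, over 48 weeks: SAEs in 29/84 = 34.5% (printed as 35%) and 23/90 = 25.6% (printed as 26%).

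**Scaling to 12 weeks (assumption: constant hazard).** Risk over 12 weeks = 1 − (1 − p)^(12/48).
- Active: 1 − 0.65^0.25 = 10.2%, and 32 × 0.102 = 3.3 participants.
- Placebo: 1 − 0.74^0.25 = 7.3%, and 16 × 0.073 = 1.2 participants.
- Total: about 4.4 participants with an SAE before rounding. Difference: 2.9 points.

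**Sampling error.** 95% half-width = 1.96 × √(0.102 × 0.898/32 + 0.073 × 0.927/16) = 16.5 points.

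**The filter.** Let f be the share of participants with an SAE who are lost to the rule, equal in both arms because the judgement is blinded. Each rate becomes p(1 − f), and so the difference shrinks by the factor (1 − f). The documents give no value for f; 25% to 75% is assumed. As an upper scenario, the second set of columns carries the full 48-week rates into the trial (11.0 + 4.1 = 15.1 participants; half-width about 27 points).

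| f | Participants lost, 12-week rates (of 4.4) | Visible difference, 12-week rates | Visible difference, 48-week rates |
|---|---|---|---|
| 0 | 0 | 2.9 points | 9.0 points |
| 25% | 1.1 | 2.2 | 6.7 |
| 50% | 2.2 | 1.5 | 4.5 |
| 75% | 3.3 | 0.7 | 2.2 |

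If the whole excess looked like MSA and every such event were filtered, the visible difference would be 0.

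**Passages side by side.**
1. Within Appendix 3, expected signs and symptoms are out and exacerbations of a pre-existing condition are in. A worsening of MSA fits both entries.
2. Appendix 3 creates a class of disease-related events that are not AEs. Protocol 8.3.6 says the topic does not apply.
3. SAP 3.5 and 5 rely on every abnormal finding becoming an AE. Appendix 3 excludes disease-associated findings that are not worse than expected, and otherwise requires the investigator to judge a finding clinically significant. The stated reason for dropping the shift tables of Protocol 9.4.1.2 and 9.4.1.5 therefore fails.

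**The case against.** Much can be said for the plan.

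- **The exclusion is narrow.** A reader might infer that Appendix 3 removes all MSA signs, symptoms, hospitalisations and progression deaths. It does not. Only expected ones go, worse-than-expected ones stay, and exacerbations are AEs. The text is ambiguous about a deterioration; it does not order its exclusion.
- **Eligibility limits what is expected.** Protocol 5.1 requires an anticipated survival of at least 3 years. Protocol 5.2 excludes severe orthostatic symptoms, falls more than once a week and confinement to bed or, all day, to a wheelchair. A progression death within 12 weeks would be hard to call expected.
- **The 12-week rationale is not a contradiction.** Protocol 4.2 calls the treatment period "short enough that disease progression is unlikely to be a confounder". One might infer that this clashes with Appendix 3. It is better read as leaving little that could qualify as expected progression, although it does not narrow expected signs and symptoms.
- **The stated test is not disease versus drug.** It is expected versus worse than expected. Causality is a separate step for recorded events.
- **Other arm comparisons remain.** UMSARS Parts I to IV are summarised by arm, and Part III includes resting and standing blood pressure and orthostatic symptoms. Vital signs, ECG interpretation, laboratory changes, examinations and withdrawals with reasons are reported too.

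The first four points stand and limit the concern. The fifth gives partial cover only. Protocol vital signs are taken supine, UMSARS Part III is measured at scheduled visits and summarised descriptively, and none of these records a hospitalisation. A death classed as progression would appear only in disposition.

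**Conclusion.** The concern holds in a limited form. Investigator judgement can keep some serious MSA-like events out of the TEAE, SAE and death rows that serve the primary objective. The text gives that judgement little guidance and contradicts itself across Appendix 3, Protocol 8.3.6 and SAP 3.5 and 5. If the filter works equally in both arms, it pulls a true excess toward zero, which is the favourable direction for a safety conclusion.

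The size is unknown. With about 4 to 5 participants expected to have an SAE, losing one or two would matter to a descriptive account of serious events. That expectation rests on constant hazard and on carrying rates over from a trial of another drug, whose own handling of disease events the documents do not describe. The share lost is an assumption.

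A reader might go further and infer that a harm would be hidden and the tolerability conclusion changed. The documents do not support that. In every scenario above, the shrinkage is well inside the sampling error (2.9 points at most against 16.5; 9.0 at most against 27), safety is descriptive with no formal hypothesis, and other endpoints would show part of any orthostatic or motor worsening. The point should be fixed because the remedy is cheap and the filter is avoidable. It is not a must-fix.

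**What to change.** 1. Reconcile Appendix 3 with Protocol 8.3.6 and with SAP 3.5 and 5, and settle within Appendix 3 how the exacerbation entry and the expected-symptom entry apply to MSA itself.
2. Record every death and every hospitalisation on the AE/SAE page whatever the attribution, with a yes/no flag for whether the investigator considers it disease-related. Attribution is then kept as data and no longer acts as a filter.
3. In SAP 3.5.1, tabulate all deaths and all serious events by arm regardless of the flag, with flagged events as a separate row.
4. Restore the shift tables of Protocol 9.4.1.2 and 9.4.1.5, since their removal rests on AE capture that Appendix 3 does not provide.
5. If sites are already closed, retrieve deaths and hospitalisations from source documents before database lock. The End of Study CRF is described only as holding withdrawals and reasons, so it cannot be relied on for hospitalisations.

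The cost is amended wording, one CRF field, a few extra tables and a few more SAE reports, most of them disease-related. Limiting the new recording to deaths and hospitalisations avoids crowding the TEAE tables with every MSA sign. Nothing here changes patient management.

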10.4. Appendix 4: Contraceptive Guidance and Collection of Pregnancy Information

Definitions:

Woman of Childbearing Potential (WOCBP)

A woman is considered fertile following menarche and until becoming post-menopausal unless permanently sterile (see below).

Women in the following categories are not considered WOCBP

- 1. Premenarchal
- 2. Premenopausal female with 1 of the following:
 - Documented hysterectomy
 - Documented bilateral salpingectomy
 - Documented bilateral oophorectomy

Note: Documentation can come from the site personnel's: review of the participant's medical records, medical examination, or medical history interview.

3. Postmenopausal female

- A postmenopausal state is defined as no menses for 12 months without an alternative medical cause. A high follicle stimulating hormone (FSH) level in the postmenopausal range may be used to confirm a postmenopausal state in women not using hormonal contraception or hormonal replacement therapy (HRT). However, in the absence of 12 months of amenorrhea, a single FSH measurement is insufficient.
- Females on HRT and whose menopausal status is in doubt will be required to use one of the non-estrogen hormonal highly effective contraception methods if they wish to continue their HRT during the study. Otherwise, they must discontinue HRT to allow confirmation of postmenopausal status before study enrollment.

Contraception Guidance:

Female participants

Female participants of childbearing potential are eligible to participate if they agree to use a highly effective method of contraception consistently and correctly as described in Table 2.

Table 2: Highly Effective Contraceptive Methods

Table 2: Highly Effective Contraceptive Methods

Highly Effective Contraceptive Methods That Are User Dependent ^a

Failure rate of <1% per year when used consistently and correctly.

Combined (estrogen and progestogen containing) hormonal contraception associated with inhibition of ovulation^b

- Oral
- Intravaginal
- Transdermal

Progestogen only hormonal contraception associated with inhibition of ovulation

- Oral
- Injectable

Highly Effective Methods That Are User Independent a

Implantable progestogen only hormonal contraception associated with inhibition of ovulation^b

- Intrauterine device (IUD)
- Intrauterine hormone-releasing system (IUS)
- Bilateral tubal occlusion

Vasectomized partner

A vasectomized partner is a highly effective contraception method provided that the partner is the sole male sexual partner of the WOCBP and the absence of sperm has been confirmed. If not, an additional highly effective method of contraception should be used.

Sexual abstinence

Sexual abstinence is considered a highly effective method only if defined as refraining from heterosexual intercourse during the entire period of risk associated with the study intervention. The reliability of sexual abstinence needs to be evaluated in relation to the duration of the study and the preferred and usual lifestyle of the participant.

NOTES:

- a) Typical use failure rates may differ from those when used consistently and correctly. Use should be consistent with local regulations regarding the use of contraceptive methods for participants participating in clinical studies.
- b) Hormonal contraception may be susceptible to interaction with the study intervention, which may reduce the efficacy of the contraceptive method.

Pregnancy Testing:

- WOCBP should only be included after a negative urine pregnancy test.
- Pregnancy testing will be performed whenever a menstrual cycle is missed or when pregnancy is otherwise suspected

Collection of Pregnancy Information:

• The investigator will collect pregnancy information on any female participant who becomes pregnant while participating in this study. Information will be recorded on the appropriate form and submitted to the sponsor within 24 hours of learning of a participant's pregnancy.

The participant will be followed to determine the outcome of the pregnancy. The investigator will collect follow-up information on the participant and the neonate and the information will be forwarded to the sponsor. Generally, follow-up will not be required for longer than 6 to 8 weeks beyond the estimated delivery date. Any termination of pregnancy will be reported, regardless of fetal status (presence or absence of anomalies) or indication for the procedure.

- While pregnancy itself is not considered to be an AE or SAE, any pregnancy complication or elective termination of a pregnancy will be reported as an AE or SAE. A spontaneous abortion is always considered to be an SAE and will be reported as such. Any post-study pregnancy related SAE considered reasonably related to the study intervention by the investigator will be reported to the sponsor as described in Section 8.3.4. While the investigator is not obligated to actively seek this information in former study participants, he or she may learn of an SAE through spontaneous reporting.
- Any female participant who becomes pregnant while participating in the study will be withdrawn from the study.

10.5. Appendix 5: Abbreviations

Abbreviation Definition

AE Adverse Event

ANCOVA Analysis of Covariance

CGI-C Clinical Global Impression of Change

CGI-S Clinical Global Impression of Severity

CRO Contract Research Organization

ECG Electrocardiogram

eCRF electronic Case Report Form

EMA European Medicines Agency

EOT End of Treatment

ET Early Termination

GCP Good Clinical Practice

ICH International Conference on Harmonization

IR Immediate Release

ITT Intent-To-Treat

MAO-B Monoamine Oxidase-B

mg Milligrams

mL Milliliters

MoCA Montreal Cognitive Assessment scale

MRI Magnetic Resonance Imaging

MSA Multiple System Atrophy

MSA-QoL Multiple System Atrophy-Quality of Life scale

od once daily

PD Parkinson's disease

PGI-C Patient Global Impression of Change

PGI-S Patient Global Impression of Severity

SAE Serious Adverse Event

SNRI Serotonin-norepinephrine Reuptake Inhibitor

SOC System Organ Class
SoC Standard of Care

SSRI Selective Serotonin Reuptake Inhibitor

SUSAR Suspected Unexpected Serious Adverse Reactions

TEAE Treatment-emergent Adverse Event

UDRS Unified Dystonia Rating Scale

UMSARS Unified Multiple System Atrophy Rating Scale

WOCBP Women of child bearing potential

Protocol Title: A 12-WEEKS, MULTICENTRE, RANDOMIZED, DOUBLE-BLIND, PLACEBO-CONTROLLED, EXPLORATORY, PILOT STUDY TO EVALUATE THE SAFETY AND EFFICACY OF SAFINAMIDE 200 MG ONCE DAILY, AS ADD-ON THERAPY, IN PATIENTS WITH POSSIBLE OR PROBABLE PARKINSONIAN VARIANT OF MULTIPLE SYSTEM ATROPHY

Protocol Number: Z7219K01

Amendment Number: 0

Compound Number: Safinamide

Short Title: Safinamide for Multiple System Atrophy

Sponsor Name: Zambon SpA

Legal Registered Address: [name]

[name]

Regulatory Agency Identifying Number(s):

EudraCT Number: 2018-004145-16

Approval Date: August 09, 2019

THIS DOCUMENT IS ZAMBON'S SOLE PROPERTY AND OWNERSHIP. THIS DOCUMENT, AND ALL INFORMATION AND DATA CONTAINED HEREIN HAS TO BE CONSIDERED AND TREATED AS STRICTLY CONFIDENTIAL. THIS DOCUMENT SHALL BE USED ONLY FOR THE PURPOSE OF THE DISCLOSURE HEREIN PROVIDED. NO DISCLOSURE OR PUBLICATION SHALL BE MADE WITHOUT THE PRIOR WRITTEN CONSENT OF ZAMBON.

CONFIDENTIAL

Protocol Administrative Letter #1 – August 09, 2019 Protocol Z7219K01 - Version 1.0 – February 21, 2019

Purpose

The aim of this administrative change is to clarify an inconsistency within the study protocol in regards to the number of evaluable patients, to provide additional clarifications on the sample size determination background and to provide information on the benefit/risk assessment.

1. Number of Evaluable Patients

It has been noted that in section 4.1 "Overall design" is incorrectly reported the following: "Approximately 56 participants will be screened to achieve 48 randomly assigned (2:1) to study intervention and 40 evaluable participants for an estimated total of respectively 30 and 10 evaluable participants per intervention group."

We confirm that, as correctly reported in all the other sections of the protocol, approximately 56 participants will be screened to achieve 48 randomly assigned to study intervention and 40 evaluable participants for an estimated total of respectively 26 and 14 evaluable participants per intervention group.

The inconsistency within the document will be corrected with the first protocol amendment.

2. Sample Size Determination Background

The primary objective of the current study is to evaluate safety of salfinamide 200 mg once daily compared to placebo. This is the first formal evaluation of salfinamide in this population in a double blind, placebo controlled study, so a pilot study was deemed advisable prior to an adequately powered efficacy study. As the primary objective of the study is evaluation of safety, no formal sample size calculations have been made to justify sample size.

The sample size was selected based on previous studies in this population and the safety profile of salfinamide in the marketed indication of Parkinson's Disease. The current study enrolls 26 active vs 14 placebo. While there are few recent efficacy studies of symptomatic therapy in MSA, there is a more recent study of the efficacy of rasagiline (Poewe, W., et al. (2015) "Efficacy of rasagiline in patients with the parkinsonian variant of multiple system atrophy: a randomised, placebo-controlled trial" published on *The Lancet Neurology*, 14(2), 145–152. https://doi.org/10.1016/S1474-4422(14)70288-1) that randomized 84 subjects to rasagiline and 90 to placebo. While this study failed to find a therapeutic effect of rasagiline, it demonstrated that this sample size would have been adequate to detect a clinically relevant change in symptoms. A study of that size was deemed too large as an initial safety study.

CONFIDENTIAL.

Protocol Administrative Letter #1 – August 09, 2019 Protocol Z7219K01 - Version 1.0 – February 21, 2019

Previous studies of salfinamide in Parkinson's Disease showed Adverse Event rates in treated groups to be less than 10% in excess of placebo (for example Borgohain, R, et al. (2014) "Randomized trial of safinamide add-on to levodopa in Parkinson's disease with motor fluctuations" published on *Movement Disorders*, 29(2), 229–237. https://doi.org/10.1002/mds.25751). In that occasion, it was deemed reasonable to perform a trial with approximately 40 subjects - randomized at a 2:1 ratio active: placebo – and it was judged to be sufficient to provide an estimate as to whether AEs are likely to be within this range in the MSA patient population at this dose.

3. Benefit/Risk Assessment

Safinamide has been approved by the European Medicines Agency (EMA) and the Food and Drug Administration (FDA) for the treatment of PD patients as add-on therapy to levodopa (alone or in combination with other antiparkinsonian drugs). At the current date, safinamide is on the market in 13 European countries and the USA, Canada, Australia, Brazil and Colombia. There are extensive post marketing surveillance data in PD patients for the 50mg and 100 mg doses. With regards to the current trial in which a dose of 200 mg will be taken for 12 weeks, safety data are also derived from trials performed in over 3000 subjects, including 2019 with Parkinson's disease of whom 500 were treated for more than 2 years.

For the 200 mg dose, safety data are available for 134 PD patients who had repeated doses of safinamide \geq 150mg daily. Of these, long term safety and tolerability data of up to 2 years for safinamide doses \geq 150 mg/day are available in 89 patients who took part in Study NW-1015/015/III/2003 and in the 69 who continued treatment in the double-blind, placebo-controlled, extension Study NW-1015/017/III/2003.

Doses of ≥ 150 mg/day were generally well- tolerated and no safety concerns were observed. The tolerability was similar to the 50mg and 100 mg/day doses, although the proportion of patients experiencing severe TEAEs (approx. 10%) was somewhat higher in the 150 – 200 mg group. The proportion of patients discontinuing due to TEAEs and the number of SAEs was similar for all treatment groups. The most frequent treatment-emergent adverse events (TEAEs) reported in Studies 015 and 017 were in the CNS and GI systems and are consistent with those reported in the SmPC. All TEAEs resolved without sequelae.

From the available clinical data, the safety and tolerability of the 200 mg dose in MSA patients is expected to be acceptable. Should patients not tolerate this dose, they may de-escalate to a lower dose or if they still do not tolerate the study medication, they can withdraw from the study.

